6.1.1.4.2 Concomitant Medications

The investigator or qualified designee will record medication, if any, taken by the subject during the trial. All medications related to reportable SAEs and ECIs should be recorded as defined in Section 7.2.

6.1.1.5 Disease Details and Treatments

6.1.1.5.1 Disease Details

The investigator or qualified designee will obtain prior and current details regarding disease status.

6.1.1.5.2 Prior Treatment Details

The investigator or qualified designee will review all prior cancer treatments including systemic treatments, radiation and surgeries.

6.1.1.5.3 Subsequent Anti-Cancer Therapy Status

The investigator or qualified designee will review all new anti-neoplastic therapy initiated after the last dose of trial treatment. If a subject initiates a new anti-cancer therapy within 30 days after the last dose of trial treatment, the 30 day Safety Follow-up visit must occur before the first dose of the new therapy. Once new anti-cancer therapy has been initiated the subject will move into survival follow-up.

6.1.1.6 Assignment of Screening Number

Register of all patients invited to participate and screened is going to be held.

6.1.1.7 Assignment of Trial Identification Number

Each patient is going to be registered with a number for confidentiality purposes. No randomization is going to take place.

6.1.1.8 Trial Compliance (Medication/Diet/Activity/Other)

Trial compliance is going to be monitored via scheduled visits.

6.1.2 Clinical Procedures/Assessments

See trial flow chart (section 6.0).

6.1.2.1 Adverse Event (AE) Monitoring

The investigator or qualified designee will assess each subject to evaluate for potential new or worsening AEs as specified in the Trial Flow Chart and more frequently if clinically indicated. Adverse experiences will be graded and recorded throughout the study and during the follow-up period according to NCI CTCAE Version 4.0 (see Section 11.2). Toxicities will be characterized in terms regarding seriousness, causality, toxicity grading, and action taken with regard to trial treatment.

For subjects receiving treatment with pembrolizumab all AEs of unknown etiology associated with pembrolizumab exposure should be evaluated to determine if it is possibly an event of clinical interest (ECI) of a potentially immunologic etiology (termed immune-related adverse events, or irAEs); see the separate ECI guidance document in Appendix 4 regarding the identification, evaluation and management of potential irAEs.

Please refer to section 7.2 for detailed information regarding the assessment and recording of AEs.

6.1.2.2 Full Physical Exam

The investigator or qualified designee will perform a complete physical exam during the screening period. Clinically significant abnormal findings should be recorded as medical history. A full physical exam should be performed during screening,

6.1.2.3 Directed Physical Exam

For cycles that do not require a full physical exam per the Trial Flow Chart, the investigator or qualified designee will perform a directed physical exam as clinically indicated prior to trial treatment administration.

6.1.2.4 Vital Signs

The investigator or qualified designee will take vital signs at screening, prior to the administration of each dose of trial treatment and at treatment discontinuation as specified in the Trial Flow Chart (Section 6.0). Vital signs should include temperature, pulse, respiratory rate, weight and blood pressure. Height will be measured at screening only.

6.1.2.5 Eastern Cooperative Oncology Group (ECOG) Performance Scale

The investigator or qualified designee will assess ECOG status (see Section 11.1) at screening, prior to the administration of each dose of trial treatment and discontinuation of trial treatment as specified in the Trial Flow Chart.

6.1.2.6 Tumor Imaging and Assessment of Disease

CT scan imaging to be undertaken every 9 weeks (3 cycles of treatment) for the first year and every 12 weeks (4 cycles) from the second year onwards for patients whilst on treatment, or for patients who discontinue trial treatment for reasons other than disease progression.

6.1.2.7 Tumor Tissue Collection and Correlative Studies Blood Sampling

PDL1 status to be undertaken from histological sample available at diagnosis of metastatic disease (pre- first line chemotherapy sample) and also from a new biopsy after first line chemotherapy and prior to study entry.

6.1.3 Laboratory Procedures/Assessments

Details regarding specific laboratory procedures/assessments to be performed in this trial are provided below Laboratory Safety Evaluations (Hematology, Chemistry and Urinalysis)

Laboratory tests for hematology, chemistry, urinalysis, and others are specified in Table 5.

Table 5 Laboratory Tests

Hematology	Chemistry	Urinalysis	Other
FBC	Albumin	Blood	Serum β -human chorionic gonadotropin †
Hemoglobin	Alkaline phosphatase	Glucose	(β -hCG)†
Platelet count	Alanine aminotransferase (ALT)	Protein	PT (INR)
WBC (total and differential)	Aspartate aminotransferase (AST)	Specific gravity	aPTT
Absolute Neutrophil Count	Lactate dehydrogenase (LDH)	Microscopic exam (If abnormal)	Free thyroxine (T4)
Absolute Lymphocyte Count	Uric Acid	results are noted	Thyroid stimulating hormone (TSH)
	Calcium	Urine pregnancy test †	ACTH
	Chloride		Cortisol (morning sample)
	Glucose		
	Phosphorus		
	Potassium		
	Sodium		
	Magnesium		
	Total Bilirubin		
	Direct Bilirubin (If total bilirubin is elevated above the upper limit of normal)		

† Perform on women of childbearing potential only. If urine pregnancy results cannot be confirmed as negative, a serum pregnancy test will be required.

SWIPE Protocol Version: 1.1 June, 2017

Laboratory tests for screening or entry into the Second Course Phase should be performed within 10 days prior to the first dose of treatment. After Cycle 1, pre-dose laboratory procedures can be conducted up to 72 hours prior to dosing. Results must be reviewed by the investigator or qualified designee and found to be acceptable prior to each dose of trial treatment.

6.1.3.1 Pharmacokinetic/Pharmacodynamic Evaluations

No pharmacokinetic or pharmacodynamic evaluations are going to be carried out.

6.1.3.1.1 Blood Collection for Serum Pembrolizumab

Not applicable

6.1.3.1.2 Blood Collection for Anti-Pembrolizumab Antibodies

Not applicable

6.1.4 Other Procedures

6.1.4.1 Withdrawal/Discontinuation

When a subject discontinues/withdraws prior to trial completion, all applicable activities scheduled for the final trial visit should be performed at the time of discontinuation. Any adverse events which are present at the time of discontinuation/withdrawal should be followed in accordance with the safety requirements outlined in Section 7.2 - Assessing and Recording Adverse Events. Subjects who a) attain a CR or b) complete 24 months of treatment with pembrolizumab may discontinue treatment with the option of restarting treatment if they meet the criteria specified in Section 7.1.5.5. After discontinuing treatment following assessment of CR, these subjects should return to the site for a Safety Follow-up Visit (described in Section 7.1.5.3.1) and then proceed to the Follow-Up Period of the study (described in Section 7.1.5.4).

6.1.4.2 Blinding/Unblinding

Not applicable.

6.1.5 Visit Requirements

Visit requirements are outlined in Section 6.0 - Trial Flow Chart. Specific procedure-related details are provided above in Section 7.1 - Trial Procedures.

6.1.5.1 Screening

Patients with metastatic NSCLC who have not progressed after first line chemotherapy, are going to be identified by the treating oncologists, [name], [name]

and [name]. Following initial discussion about proposed study, patients are going to be referred to the Clinical Trials Unit staff, to undertake screening for the study.

6.1.5.1.1 Screening Period

Aim to start in January 2016 and finish once all forty-eight (48) patients have been enrolled, with a target date to finish accrual in July 2017.

6.1.5.2 Treatment Period

Aim to start treatment in January 2016. Patients to receive treatment until either progressive disease or until they have received two (2) years of continuous Pembrolizumab treatment.

6.1.5.3 Post-Treatment Visits

See flow chart (section 6.0).

7.1.5.3.1 Safety Follow-Up Visit

The mandatory Safety Follow-Up Visit should be conducted approximately 30 days after the last dose of trial treatment or before the initiation of a new anti-cancer treatment, whichever comes first. All AEs that occur prior to the Safety Follow-Up Visit should be recorded. Subjects with an AE of Grade > 1 will be followed until the resolution of the AE to Grade 0-1 or until the beginning of a new anti-neoplastic therapy, whichever occurs first. SAEs that occur within 90 days of the end of treatment or before initiation of a new anti-cancer treatment should also be followed and recorded. Subjects who are eligible for retreatment with pembrolizumab (as described in Section 7.1.5.5) may have up to two safety follow-up visits, one after the Treatment Period and one after the Second Course Phase.

6.1.5.4 Follow-up Visits

Subjects who discontinue trial treatment for a reason other than disease progression will move into the Follow-Up Phase and should be assessed every 9 weeks (63 ± 7 days) by radiologic imaging to monitor disease status. After 1 year, the imaging time point will occur every 12 weeks (84 ± 7 days). Every effort should be made to collect information regarding disease status until the start of new anti-neoplastic therapy, disease progression, death, end of the study or if the subject begins retreatment with pembrolizumab as detailed in Section 7.1.5.5. Information regarding post-study anti-neoplastic treatment will be collected if new treatment is initiated.

Subjects who are eligible to receive retreatment with pembrolizumab according to the criteria in Section 7.1.5.5 will move from the follow-up phase to the Second Course Phase when they experience disease progression.

6.1.5.4.1 Survival Follow-up

Once a subject experiences confirmed disease progression or starts a new anti-cancer therapy, the subject moves into the survival follow-up phase and should be contacted by telephone every 12 weeks to assess for survival status until death, withdrawal of consent, or the end of the study, whichever occurs first.

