3.2.3 Rationale for Endpoints

3.2.3.1 Efficacy Endpoints

Primary endpoint: percentage of patients that have not progressed at 1 year using immune related radiological criteria (see section 11.3). The 1 year timing relates to the time from trial enrolment and initiation of pembrolizumab as maintenance therapy. This is the most clinically relevant endpoint in a maintenance study. Prolongation of disease control is a very worthwhile endpoint, towards the realization of the goal to obtain long term disease control for patients with metastatic NSCLC, similar to the results seen with checkpoint inhibition for patients with melanoma. The timing of assessment at 1 year is based on the durable nature of responses seen with Pembrolizumab so far, suggesting that at 1 year there is going to be a large difference in disease progression between patients on Pembrolizumab compared to the historical data from the maintenance studies.

Secondary Endpoints: These would include

- Response rates (RECIST)
- Response Rates with immune related Response Criteria (irRC)
- Radiological Progression Free Survival (PFS) using RECIST criteria
- Immune-related PFS using irRC: irPFS is the progression free survival (PFS) measured applying immune related radiological criteria. PFS (RECIST) at 6 months and 1 year from initiation of Pembrolizumab.
- Overall survival
- 1, 2 and 3 year OS rate.
- Best overall response rate and disease control rate using both RECIST and irRC in patients with squamous and non-squamous NSCLC and
- Immune-related toxicities (IRAEs)

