4.2.1.2 Dose Modification (Escalation/Titration/Other)

Adverse events (both non-serious and serious) associated with pembrolizumab exposure may represent an immunologic etiology. These adverse events may occur shortly after the first dose or several months after the last dose of treatment. Pembrolizumab must be withheld for drug-related toxicities and severe or life-threatening AEs as per 3 below. See Section 5.6 for supportive care guidelines, including use of corticosteroids.

Table 3 Dose Modification Guidelines for Drug-Related Adverse Events

Toxicity	Hold Treatment For Grade	Timing for Restarting Treatment	Treatment Discontinuation
Diarrhea/Colitis	2-3	Toxicity resolves to Grade 0-1	Toxicity does not resolve within 12 weeks of last dose or inability to reduce corticosteroid to 10 mg or less of prednisone or equivalent per day within 12 weeks
	4	Permanently discontinue	Permanently discontinue
AST, ALT, or Increased Bilirubin	2	Toxicity resolves to Grade 0-1	Toxicity does not resolve within 12 weeks of last dose
	3-4	Permanently discontinue (see exception below) ^a	Permanently discontinue
Type 1 diabetes mellitus (if new onset) or Hyperglycemia	T1DM or 3-4	Hold pembrolizumab for new onset Type 1 diabetes mellitus or Grade 3-4 hyperglycemia associated with evidence of beta cell failure	Resume pembrolizumab when patients are clinically and metabolically stable
Hypophysitis	2-4	Toxicity resolves to Grade 0-1. Therapy with pembrolizumab can be continued while endocrine replacement therapy is instituted	Toxicity does not resolve within 12 weeks of last dose or inability to reduce corticosteroid to 10 mg or less of prednisone or equivalent per day within 12 weeks
Hyperthyroidism	3	Toxicity resolves to Grade 0-1	Toxicity does not resolve within 12 weeks of last dose or inability to reduce corticosteroid to 10 mg or less of prednisone or equivalent per day within 12 weeks
	4	Permanently discontinue	Permanently discontinue
Hypothyroidism		Therapy with pembrolizumab can be continued while thyroid replacement therapy is instituted	Therapy with pembrolizumab can be continued while thyroid replacement therapy is instituted
Infusion Reaction	2 ^b	Toxicity resolves to Grade 0-1	Permanently discontinue if toxicity develops despite adequate premedication
	3-4	Permanently discontinue	Permanently discontinue

Toxicity	Hold Treatment For Grade	Timing for Restarting Treatment	Treatment Discontinuation

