The End of Treatment and Follow-up visit procedures are listed in Section 6 (Protocol Flow Chart) and Section 7.1.5 (Visit Requirements). After the end of treatment, each subject will be followed for 30 days for adverse event monitoring (serious adverse events will be collected for 90 days after the end of treatment as described in Section 7.2.3.1). Subjects who discontinue for reasons other than progressive disease will have post-treatment follow-up for disease status until disease progression, initiating a non-study cancer treatment, withdrawing consent or becoming lost to follow-up. After documented disease progression each subject will be followed by telephone for overall survival until death, withdrawal of consent, or the end of the study, whichever occurs first.

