5.0 TRIAL FLOW CHART

5.1 Study Flow Chart

Trial Period:	Screening Phase		Treatment Cycles ^a								End of Treatment	Post-Treatment		
	Pre-screening (Visit 1)	Main Study Screening (Visit 2)	1	2	3	4	To be repeated beyond 8 cycles					Safety Follow-up	Follow Up Visits ^b	Survival Follow-Up
Treatment Cycle/Title:			5	6	7	8								
Scheduling Window (Days):		-28 to -1		± 3	± 3	± 3	± 3	± 3	± 3	± 3	At time of Discon	30 days post discon	Every 9 weeks post discon	Every 12 weeks
Administrative Procedures														
Pre-screening Consent	✓													
Informed Consent		✓												
Inclusion/Exclusion Criteria	✓	✓												
Demographics and Medical History	✓	✓												
Prior and Concomitant Medication Review	✓	✓	✓	✓	✓	✓	✓	✓	✓	✓	✓			
Trial Treatment Administration			✓	✓	✓	✓	✓	✓	✓	✓				
Post-study anticancer therapy status												✓	✓	✓
Survival Status			✓	✓	✓	✓	✓	✓	✓	✓	✓	✓	✓	✓
Clinical Procedures/Assessments														
Review Adverse Events				✓	✓	✓	✓	✓	✓	✓	✓	✓	✓	
Full Physical Examination	✓	✓	✓		✓		✓		✓		✓	✓	✓	
Directed Physical Examination				✓		✓		✓		✓	✓	✓	✓	

Trial Period:	Screening Phase		Treatment Cycles ^a								End of Treatment	Post-Treatment		
			1	2	3	4	To be repeated beyond 8 cycles							
Treatment Cycle/Title:	Pre-screening (Visit 1)	Main Study Screening (Visit 2)					5	6	7	8	Discon	Safety Follow-up	Follow Up Visits ^b	Survival Follow-Up
Scheduling Window (Days):		-28 to -1		± 3	± 3	± 3	± 3	± 3	± 3	± 3	At time of Discon	30 days post discon	Every 9 weeks post discon	Every 12 weeks
Vital Signs and Weight		√	√	√	√	√	√	√	√	√	√	√		
ECOG Performance Status	√	√	√	√	√	√	√	√	√	√	√	√		
Laboratory Procedures/Assessments: analysis performed by LOCAL laboratory														
Pregnancy Test – Urine or Serum β-HCG	√	√	√	√	√	√	√	√	√	√	√			
PT/INR and aPTT	√		√	√	√	√	√	√	√	√	√			
CBC with Differential	√	√	√	√	√	√	√	√	√	√	√			
Comprehensive Serum Chemistry Panel	√	√	√	√	√	√	√	√	√	√	√			
Urinalysis	√													
T3, FT4 and TSH	√		√	√	√	√	√	√	√	√	√			
Efficacy Measurements														
Tumor Imaging			√			√			√		√		√	
Tumor Biopsies/Archival Tissue Collection/Correlative Studies Blood														
Newly Obtained Tissue Collection			√											

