6.2.3 Immediate Reporting of Adverse Events to the Sponsor and to Merck

6.2.3.1 Serious Adverse Events

A serious adverse event is any adverse event occurring at any dose or during any use of Merck's product that:

- Results in death;
- Is life threatening;
- Results in persistent or significant disability/incapacity;
- Results in or prolongs an existing inpatient hospitalization;
- Is a congenital anomaly/birth defect;
- Is another important medical event

• **Note:** In addition to the above criteria, adverse events meeting either of the below criteria, although not serious per ICH definition, are reportable to the Merck in the same timeframe as SAEs to meet certain local requirements. Therefore, these events are considered serious by Merck for collection purposes.

- Is a new cancer (that is not a condition of the study);
- Is associated with an overdose.

Refer to Table 6 for additional details regarding each of the above criteria.

For the time period beginning when the consent form is signed until treatment allocation/randomization, any serious adverse event, or follow up to a serious adverse event, including death due to any cause other than progression of the cancer under study (reference Section 7.2.3.3 for additional details) that occurs to any subject must be reported within 24 hours to the Sponsor and within 2 working days to Merck Global Safety if it causes the subject to be excluded from the trial, or is the result of a protocol-specified intervention, including but not limited to washout or discontinuation of usual therapy, diet, placebo treatment or a procedure.

For the time period beginning at treatment allocation/randomization through 90 days following cessation of treatment, or 30 days following cessation of treatment if the subject initiates new anticancer therapy, whichever is earlier, any serious adverse event, or follow up to a serious adverse event, including death due to any cause other than progression of the cancer under study (reference Section 7.2.3.3 for additional details), whether or not related to the Merck product, must be reported within 24 hours to the Sponsor and within 2 working days to Merck Global Safety.

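### For patients who stop for progression and start no new therapy, no scheduled contact asks about adverse events between the 30-day safety visit and day 90, so late SAEs and ECIs may be under-ascertained

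*Combined protocol and SAP*

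**What the plan says.** All references are to the combined protocol and SAP.

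- **Route after progression.** Under section 6.1.5.4.1, confirmed progression or the start of other cancer treatment puts a patient into survival follow-up. From then on the patient "should be contacted by telephone every 12 weeks to assess for survival status until death". Section 4.8 agrees: "After documented disease progression each subject will be followed by telephone for overall survival until death".
- **Flow chart (5.1).** The row "Review Adverse Events" is ticked for cycles 2 to 8, discontinuation, the 30-day safety visit and the 9-weekly follow-up visits. It is blank under survival follow-up, where only survival status and post-study anticancer therapy are ticked.
- **Safety visit (7.1.5.3.1).** "The mandatory Safety Follow-Up Visit should be conducted approximately 30 days after the last dose of trial treatment", or earlier if new therapy starts.
- **Who has the 9-weekly visits (6.1.5.4).** Patients who stop for a reason other than progression.
- **Reporting duty.** Section 6.2.3.1 sets the SAE period: "For the time period beginning at treatment allocation/randomization through 90 days following cessation of treatment", cut to 30 days if new anticancer therapy begins. Section 6.2.3.2 gives ECIs the same period. Sections 4.8 and 7.1.5.3.1 also require SAEs to be collected to day 90. All adverse events, serious or not, are required only to day 30 (6.2).
- **Late onset.** Section 4.2.1.2, on events that may be immunologic: "These adverse events may occur shortly after the first dose or several months after the last dose of treatment".
- **Endpoint.** Section 3.2.3.1 lists immune-related toxicity as a secondary endpoint and gives no time window. Section 6.1.2.1 treats events of possible immunologic cause as potential ECIs.

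**The concern.** The reporting window and the contact schedule do not match for one group. A patient who stops for progression and has no further anticancer therapy stays inside the SAE/ECI window until day 90. After the 30-day visit, however, the only planned contact is a call about survival. A new serious immune-related event in that interval is recorded only if the patient or another hospital reports it.

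A patient who stops without progression is asked about adverse events at visits that span the same interval. Ascertainment of late serious toxicity therefore depends on the efficacy outcome, and any error is towards too few events among progressors. This bears on the toxicity endpoint and on safety oversight, because section 4.10 makes the incidence and severity of adverse reactions a ground for stopping the trial early.

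**Working it through.** **Plan's own figure.** The point rests on no stated calculation. N is used only to size the group. Fleming's one-stage formula with p0 = 0.12, p1 = 0.25, one-sided α = 0.05 and power 0.80 (section 7.2; sidedness is not stated there) gives

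n = [(1.645 × √(0.12 × 0.88) + 0.842 × √(0.25 × 0.75)) / 0.13]² = 47.8, rounded up to 48, which reproduces the plan.

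**Scheduled adverse event questions after treatment**

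| Period after last dose | Stopped for progression, no new therapy | Stopped for another reason |
|---|---|---|
| To about day 30 | Discontinuation and safety visit | Discontinuation and safety visit |
| Days 31–90 | None | 9-weekly visit at day 63 ± 7; the next, at day 126, looks back over the rest |
| SAE/ECI duty | To day 90 | To day 90 |

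The 9-weekly visits are counted from discontinuation, as in the flow chart.

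**Length of the gap.** 90 − 30 = 60 days, and 60/90 = 67% of the post-treatment window. If new therapy starts by day 30, the window closes at day 30 and the gap is 0.

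**Timing of the first survival call.** The documents give the interval but not its start.
- From discontinuation: 12 × 7 = day 84, six days before the window closes.
- From the safety visit: 30 + 84 = day 114, after it closes.

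As written, neither call includes an adverse event question.

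**Share of the whole safety period.** At the planned average of 6 cycles:
- By cycle length: (6 × 21 + 30)/(6 × 21 + 90) = 156/216 = 72% lies under scheduled review.
- From first to last dose: (5 × 21 + 30)/(5 × 21 + 90) = 135/195 = 69%.
- For a patient stopping after 3 cycles, when the first 9-weekly scan is due: (63 + 30)/(63 + 90) = 93/153 = 61%.

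The 30-day window for all adverse events is fully covered.

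**Number of patients.** Patients not progression-free at 1 year: 48 × (1 − 0.25) = 36 under the target rate, and 48 × (1 − 0.12) = 42.2, about 42, under the null rate. These counts include deaths and patients treated beyond progression. The share alive and not on new therapy is not in the documents, so it is assumed:

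| Assumed share | Of 36 | As share of 48 | Of 42 |
|---|---|---|---|
| 25% | 9 | 19% | about 11 |
| 50% | 18 | 38% | 21 |
| 75% | 27 | 56% | about 32 |

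**Uncovered share of safety time among progressors.** With share s and 6 cycles it is 60s/(156 + 60s): 15/171 = 9%, 30/186 = 16% and 45/201 = 22% for s = 25%, 50% and 75%.

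**The case against.** The strongest reply is that the plan already requires what is said to be missing. SAEs to day 90 must be followed and recorded, and adverse events above Grade 1 are followed until they resolve or new therapy starts (7.1.5.3.1). ECIs are reportable to day 90 (6.2.3.2), and drug-related SAEs at any time they come to the investigator's notice (6.2.3.1). Section 6.1.2.1 speaks of recording during follow-up. This stands as far as it goes: the duty to collect exists. What is absent is a planned occasion to ask. Following open events does not find new ones, and the any-time rule depends on someone telling the investigator.

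A second reply is that 60 days is an upper limit. The flow chart times the safety visit from discontinuation, while 7.1.5.3.1 times it from the last dose. Discontinuation follows confirmed progression (4.8), and confirmation takes a second scan at least four weeks later (10.3). If the last dose came 28 days before discontinuation, the flow-chart visit would fall at 28 + 30 = day 58, leaving 32 days. This also stands, hence the wording up to 60.

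Third, the SAP plans no comparison of toxicity between progressors and others, and patients who stop for toxicity without progression do have adverse event review afterwards. That limits the consequence but does not remove the uneven ascertainment.

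Flow-chart footnotes could qualify a blank cell, but sections 4.8 and 6.1.5.4.1 limit the calls to survival independently of the chart.

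**Conclusion.** The point holds in a limited form. For patients who stop for progression and start no new anticancer therapy, up to 60 of the 90 days in the SAE/ECI window have no scheduled adverse event question, whereas patients who stop without progression are asked. Late serious events may be under-ascertained as a result. The size of any undercount cannot be computed, because the documents give neither the rate of late events nor the share of progressors who go without new therapy. The 9, 18 or 27 patients are illustrations on assumed shares. The sample size and primary endpoint are untouched.

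A reader might infer more than the documents support:

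- *That the immune-related toxicity endpoint goes largely unmeasured.* It does not. Review is scheduled at every cycle from cycle 2, at discontinuation and at day 30, which is about 70% of the whole SAE/ECI period at 6 cycles.
- *That most patients are affected.* The 36 to 42 include deaths, patients treated beyond progression and patients whose window closes at day 30 on new therapy.
- *That the hepatic ECI cannot be detected because laboratory tests end at discontinuation.* Its definition also admits unscheduled tests, and the tests end there for everyone, so they create no difference by efficacy outcome.
- *That the blank cells at screening and cycle 1 are a similar hole.* Section 6.2 already requires procedure-related events to be reported from consent, and all events to be recorded at each examination from allocation.

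**What to change.** In the flow chart (5.1) and section 6.1.5.4.1, add review of SAEs and ECIs, including serious immune-related events, to the first survival follow-up call for patients still within the reporting window. Time that call from the last dose, at or just after day 90 (for example day 90 + 7 days), so that one call covers the whole window in retrospect. Without the re-timing, a call counted from discontinuation would fall at day 84 and leave days 85–90 unasked. Patients whose window has already closed because of new therapy need no change.

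The cost is a short amendment and a few minutes on a call that already takes place. The reported late toxicity rate may come out slightly higher. No extra visit or laboratory test is needed; in particular, repeating blood tests at the 30-day visit would not cover days 31–90.
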